3.1 Study design

This is a randomized, open-label with blinded-assessment, multicenter, 52-week study to evaluate the efficacy (based on PASI 90), safety and tolerability of secukinumab 300 mg s.c. in patients with moderate to severe chronic plaque psoriasis. This study consists of 2 treatment periods: a 24-week run-in treatment period (Baseline to Week 24) and a 28-week maintenance treatment period (Week 24 to Week 52) as indicated in Figure 3-1.

For Treatment Period 1 (Baseline to Week 24) all patients will receive the same treatment:

• Secukinumab 300 mg s.c. will be self-administered at Baseline, once weekly at Week 1, 2 and 3; and thereafter every 4 weeks starting from Week 4 (ie, Week 4, 8, 12, 16 and 20).

At Week 24, all patients will be assessed in term of PASI response and either randomized to one of the 4 treatment groups in Treatment Period 2 (Week 24 to Week 52) or withdrawn from the study.

Patients with at least a 90% reduction in PASI score from Baseline will be randomized at Week 24 on a 1:1 basis to Group 1 or Group 2:

- Group 1 (recommended maintenance treatment): secukinumab 300 mg s.c. every 4 weeks (Week 24, 28, 32, 36, 40, 44 and 48).
- Group 2 (experimental dosing maintenance treatment): secukinumab 300 mg s.c. every 6 weeks (Week 24, 30, 36, 42 and 48).

Patients with less than 90% reduction in PASI score from Baseline at Week 24 but who achieved at least a 75% reduction in PASI score from Baseline are eligible for dose frequency intensification and will be randomized on a 1:1 basis to either Group 3 or Group 4:

- Group 3 (recommended maintenance treatment): secukinumab s.c. 300 mg every 4 weeks (Week 24, 28, 32, 36, 40, 44 and 48).
- Group 4 (experimental maintenance treatment): secukinumab s.c. 300 mg every 2 weeks (Week 24, 26, 28, 30, 32, 34, 36, 38, 40, 42, 44, 46 and 48).

At Week 52, patients from Group 3 and Group 4 will enter into a treatment-free follow-up period until Week 60. From the last study drug administration at Week 48 to Week 60 (12 weeks) patients will not be allowed to take any study drug. At the Week 60 visit, relapse, rebound and safety will be explored.

At Week 24, patients with a reduction in PASI score from Baseline of less than 75% will not be eligible for randomization and will be discontinued from the study.

Randomization will be stratified by body weight collected at the Randomization Visit ($< 90 \text{ kg or } \ge 90 \text{ kg}$).

[figure not shown]

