In this study, only secukinumab verum injections will be administered. This will more closely reflect a real-life situation for patients than, for example, using a double-blinded, double dummy study design that would require secukinumab placebo injections. The blinded assessor approach is enabling to capture cogent efficacy data deriving from Investigator assessments. In addition, the design supports for interpreting these Investigator assessments in the context of a patient's daily life and social function measured by PROs (EMEA/CHMP/EWP/139391/2004).

The treatment-free follow-up period will be limited to treatment Group 3 and Group 4 as treatment-free follow-up period data for drug exposures up to 300 mg s.c. every 4 weeks in the maintenance phase have already been extensively reported for the Phase 3 secukinumab program studies.

Rationale for choice of non-inferiority margin and primary endpoint

Statistical projections to support the choice of non-inferiority margin for this study are difficult as Week 24 to Week 52 data are not available for PASI 90 response rates in patients treated with the experimental dosing frequencies scheduled for this study. However, for the active controlled study CAIN457A2304 in the secukinumab development program the non-inferiority margin was set to 15%. Based on clinical judgment, a non-inferiority margin of 15% is justifiable also, especially when taking into account the maintenance phase endpoint and the maintenance responder rate (ie, 81.8% of patients achieving a PASI 90 response at Week 24 are still PASI 90 responders at Week 52) observed in the clinical trial program with secukinumab 300 mg s.c. to date. This non-inferiority margin has been accepted for the CAIN4572304 study by participating regulatory agencies in the US, EU and Japan.

Similar study designs for drug exposure reduction for other biologic treatments in moderate to severe psoriasis patients are very limited. In the rheumatoid arthritis indication, non-inferiority margins in studies with drug exposure reductions have been recently accepted up to a 20% non-inferiority margin for efficacy endpoints (den Broeder et al 2013, Mariette et al 2014).

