4.2 Exclusion criteria

Patients fulfilling **any** of the following criteria will not be eligible for inclusion in this study. No additional exclusions may be applied by the Investigator in order to ensure that the study population is representative of all eligible patients.

- 1. History of exposure to any biologic drug taken for the treatment of chronic plaque psoriasis or any other indication including but not limited to anti-tumor necrosis factor (TNF) alpha, anti-IL12/23, or any anti-IL-17A or IL-17A receptor (IL-17AR) antibody.
- 2. Use of any other investigational drug within 4 weeks prior to Baseline or within a period of 5 half-lives of the investigational drug, whichever is longer.
- 3. History of hypersensitivity to any of the study drugs or to drugs of similar chemical classes including latex hypersensitivity.
- 4. Forms of psoriasis other than chronic plaque-type (eg, pustular, erythrodermic and guttate psoriasis).
- 5. Drug-induced psoriasis (ie, new onset or current exacerbation from beta-blockers, calcium channel inhibitors or lithium).
- 6. Ongoing use of prohibited psoriasis treatments (eg, topical or systemic corticosteroids, ultraviolet (UV) therapy).
- 7. Ongoing use of other non-psoriasis prohibited treatments. Washout periods detailed in the protocol (Table 5-2) have to be adhered to. All other prior non-psoriasis concomitant treatments must be at a stable dose as detailed in the protocol before initiation of study drug.
- 8. Pregnant or nursing (lactating) women, where pregnancy is defined as the state of a female after conception and until the termination of gestation, confirmed by a positive human chorionic gonadotropin (hCG) laboratory test (> 5 mIU/mL).
- 9. Women of child-bearing potential, defined as all women physiologically capable of becoming pregnant, unless they are using effective methods of contraception during entire study or longer if required by locally approved prescribing information (e.g. in EU 20 weeks). Effective contraception methods include:
 - Total abstinence (when this is in line with the preferred and usual lifestyle of the patient. Periodic abstinence (eg, calendar, ovulation, symptothermal, post-ovulation methods) and withdrawal are not acceptable methods of contraception.
 - Female sterilization (have had surgical bilateral oophorectomy with or without hysterectomy) or tubal ligation at least 6 weeks before taking study drug.

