with the protocol, except for the chest X-ray or TB work-up, if applicable, if performed not more than 12 weeks prior to Day 1 (Baseline). If patients do not have a chest X-ray available within 12 weeks of the projected Day 1 date, the X-ray should be performed after it is certain the patient meets inclusion/exclusion criteria in order to minimize unnecessary exposure to radiation.

If the date of the TB work-up is less than 12 weeks from Baseline then the TB work-up does not have to be repeated; however, the patient must repeat the QFT performed by the central laboratory.

During the Treatment Periods 1 and 2, patients may be seen at an unscheduled visit, eg, if they experience deterioration of psoriasis or suspected AEs. During these unscheduled visits, study drug will NOT be administered.

Recommended visit windows

Treatment periods:

- ± 2 days for Baseline, Week 1, Week 2, Week 3 and Week 4 and for Week 24.
- ± 2 days for all study drug home administrations.
- \pm 5 days for all other study visits.
- Visit 1 and Visit 2 must not be conducted at the same day and all relevant information for Visit 2 must be available before treating the patient. The screening period might not be longer than 4 weeks.

For patients who discontinue study drug prematurely before the end of the Treatment Period 1 for any reason other than withdrawal of informed consent, the Week 24 (planned EOT1) visit must be performed at least 28 days (4 weeks) after the last drug administration and the patient should then enter the treatment free follow-up period, if applicable.

For patients who discontinue study drug prematurely before the end of the Treatment Period 2 for any reason other than withdrawal of informed consent, the Week 52 (planned EOT2) visit must be performed at least 28 days (4 weeks) after the last drug administration and the patient should then enter the treatment free follow-up period, if applicable.

If a patient refuses to return for these assessments or is unable to do so, every effort should be made to contact them, or a knowledgeable informant, by telephone or by sending appropriate correspondence (ie, certified letter) immediately. At this contact, the safety (eg, potential occurrence of AEs or SAEs) and the primary reason for the patient's premature withdrawal should be determined. Documentation of attempts to contact the patient should be recorded in the patient source documents.

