Vital signs	Χ	Х				Χ		Χ	Χ		Х	Χ		Χ			Χ	Х	Х	X	
Laboratory sampling: safety panel (Clinical chemistry including urine, hematology)	X	х				×		x	х		х	х		х			х	х	х	х	For processing of samples please refer to the manual of the central lab.

Period	Scr				Tre	atmen	t Perio	d 1						Treati	ment P	eriod 2	2		FU	it ^d	Comments
Visit	1	2	3	4	5	6	7	8	9	10	11	12	13	14	15	16	17	18	19	d Vis	
Week	-4 to BL °	BL	1	2	3	4	8	12	16	20	24 a, b	28	32	36	40	44	48	52 c	60	Unscheduled Visit ^d	
Recommended visit window (days)			±2	±2	±2	±2	±5	±5	±5	±5	±2	±5	±5	±5	±5	±5	±5	±5	±5	Nus	
Chest X-ray (or CT/MRI)	S																			S	Where a patient has not had a chest X-ray, chest CT or chest MRI, CT performed within 3 months prior to Screening, an image should be obtained once it is clear that the patient meets the other inclusion/exclusion criteria in order to minimize unnecessary exposure X-ray radiation.
QuantiFERON® TB-Gold In-tube test ^e	Х																			Х	see lab manual
Serum pregnancy test	Х																			Х	Only for females of child- bearing potential.
Urine pregnancy test (local)		x				x		x	x		х			x				x	x	х	In the event of a positive urine pregnancy test, study drug must be withheld and a serum pregnancy test performed at the same visit. A urine pregnancy test is not required for a woman who is sterile or who is postmenopausal.
ECG (standard 12-lead)		Х									Х							Х	Х	Х	
PASI	Х	Х	Х	Х	Х	Х	Х	Х	Х	Х	Х	Х	Х	Х	Х	Х	Х	Х	Χ	Х	
BSA	Х	Х																Х		Х	

Period	Scr				Tre	atmen	t Perio	d 1				Treatment Period 2								ita	Comments
Visit	1	2	3	4	5	6	7	8	9	10	11	12	13	14	15	16	17	18	19	d Vis	
Week	-4 to BL ^e	BL	1	2	3	4	8	12	16	20	24 a, b	28	32	36	40	44	48	52 c	60	Unscheduled Visit ^d	
Recommended visit window (days)			±2	±2	±2	±2	±5	±5	±5	±5	±2	±5	±5	±5	±5	±5	±5	±5	±5	Uns	
IGA mod 2011	Χ	Χ	Χ	Χ	Χ	Х	Χ	Х	Χ	Χ	Χ	Χ	Χ	Χ	Χ	Х	Χ	Х	Χ	Х	
DLQI		Х				Χ		Χ			Χ			Х			Χ	Х		Х	
WPAI-PSO		Х				Х		Χ			Χ			Χ			Χ	Χ		Х	
Assessment of pain, itching and scaling		Х				Х		Х			Х			Х			Х	Х		Х	
EQ-5D [©]		Х				Х		Х			Х			Х			Χ	Х		Х	
AE assessment (including injection site reactions)	х	х	х	х	х	Х	х	Х	Х	х	Х	х	х	х	х	Х	Х	Х	х	х	
Assessment of rebound																			x		Unscheduled rebound assessment only to be done at an unscheduled visit that occurs during the post-treatment follow-up period.
Randomization by IRT											Х										
IRT contact such as for registration or drug supply including home administration	х	х	х	х	х	x	х	x	х	x	х	х	x	х	x	x	x	х			

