7.3 Liver safety monitoring

To ensure patient safety and enhance reliability in determining the hepatotoxic potential of an investigational drug, a standardized process for identification, monitoring and evaluation of liver events has to be followed.

Liver events are divided into 2 categories:

- Liver events of special interest which consist of elevated transaminases and/or alkaline phosphatase and/or total bilirubin (elevated liver function tests [LFTs])
- Medically significant liver events which are considered as SAEs and which consist of marked elevations of LFTs and / or pre-specified AEs

Please refer to Table 14-1 in Appendix 2 for complete definitions of liver events.

Any liver event which meets the criteria for "medically significant" event as outlined in Table 14-1 of Appendix 2 should follow the standard procedures for SAE reporting as described in Section 7.2.

Every liver event as defined in Table 14-1 of Appendix 2 should be followed up by the Investigator/qualified site staff as summarized below. Detailed information is outlined for liver laboratory trigger in Table 14-2 in Appendix 2.

- Repeating the LFT to confirm elevation as appropriate
- Discontinuation of the investigational drug if appropriate
- Hospitalization of the patient if appropriate

- A causality assessment of the liver event via exclusion of alternative causes (eg, disease, co-medications)
- An investigation of the liver event which needs to be followed until resolution

These investigations can include serology tests, imaging and pathology assessments, and hepatologist's consultancy, based on Investigator/qualified site staff's discretion.

All follow-up information, and the procedures performed, should be recorded on appropriate eCRF pages.

7.4 **Pregnancy reporting**

To ensure patient safety, each pregnancy occurring while the patient is on study drug must be reported to Novartis within 24 hours of learning of its occurrence. The pregnancy should be followed up to determine outcome, including spontaneous or voluntary termination, details of the birth, and the presence or absence of any birth defects, congenital abnormalities, or maternal and/or newborn complications.

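### Section 7.4 makes only pregnancies on study drug reportable, so conceptions after the end of treatment need not be reported or followed, although the protocol still tests for them and asks for contraception.

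*Protocol*

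**What the plan says.** Protocol Section 7.4 (Pregnancy reporting) states the duty: "each pregnancy occurring while the patient is on study drug must be reported to Novartis within 24 hours of learning of its occurrence". It continues: "The pregnancy should be followed up to determine outcome". The second sentence refers back to the pregnancies of the first. The rest of the section says which form to use and that SAEs during a pregnancy go on the SAE form.

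Four other places bear on the time after dosing:

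- **Section 3.1**, on Groups 3 and 4: "From the last study drug administration at Week 48 to Week 60 (12 weeks) patients will not be allowed to take any study drug". Section 3.2 adds: "The treatment-free follow-up period will be limited to treatment Group 3 and Group 4".
- **Table 6-1** has urine pregnancy tests at Week 52 and Week 60. Its comment asks for a serum test at the same visit after a positive urine test. For patients who stop early, Section 6 says the end-of-treatment "visit must be performed at least 28 days (4 weeks) after the last drug administration".
- **Section 4.2, criterion 9** sets contraception "during entire study or longer if required by locally approved prescribing information (e.g. in EU 20 weeks". The amendment rationale makes clear that these 20 weeks are counted after treatment.
- **Section 7.2.2** keeps SAE reporting open until 30 days after the last visit or, where applicable, 12 weeks after the last dose. Later SAEs are reported only if the investigator suspects the drug.

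Section 6.5.6 gives an action on a positive urine test only for the treatment periods. The SAP has no pregnancy rule.

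**The concern.** The protocol treats the weeks after the last dose as relevant to pregnancy in two ways: it goes on testing, and it goes on asking for contraception. The reporting rule stops earlier. A site that follows Section 7.4 as written could confirm a pregnancy at Week 60 and have no stated duty to report it or to learn how it ends. Groups 3 and 4 are the only groups with that visit, and Group 4 received the 2-weekly regimen, which Section 3.3 says had not yet been tested in a maintenance period. At stake is the safety record of pregnancies after recent exposure. No efficacy endpoint or analysis is affected.

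**Working it through.** **Inputs.** Last dose for completers: Week 48 in every group (Protocol Section 3.1, Table 5-1). End of Treatment Period 2: Week 52 (Protocol Section 3.1, SAP Section 1.2). Patients below PASI 75 at Week 24: last dose Week 20, withdrawn at Week 24. Urine tests, read from the column positions in Table 6-1: Baseline and Weeks 4, 12, 16, 24, 36, 52 and 60.

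**Step 1: the plan's own interval.** 60 − 48 = 12 weeks, as Section 3.1 states. The Week 52 test falls 52 − 48 = 4 weeks after the last dose.

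**Step 2: end of the contraception period.** With the EU example, completers reach 48 + 20 = Week 68, and a Week 24 withdrawal reaches 20 + 20 = Week 40. Where local labelling asks for nothing longer, the period ends with the study: Week 60 in Groups 3 and 4, Week 52 in Groups 1 and 2.

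**Step 3: time outside Section 7.4,** taking being on study drug to last until the end of the treatment period.

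| Patients | Study period only | EU example |
|---|---|---|
| Groups 1 and 2 | 52 − 52 = 0 weeks | 68 − 52 = 16 weeks |
| Groups 3 and 4 | 60 − 52 = 8 weeks | 68 − 52 = 16 weeks |
| Withdrawn at Week 24 | 24 − 24 = 0 weeks | 40 − 24 = 16 weeks |

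**Step 4: four cases under Section 7.4.**

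| Conception | Found | Reportable? |
|---|---|---|
| Week 40 | Week 52 test | Yes, on any reading |
| Week 50 | Week 52 or 60 test | Depends on what being on study drug means |
| Week 54, Group 3 or 4 | Week 60 test | No |
| Week 26, withdrawn at Week 24 | Patient tells the site | No |

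The urine test before Week 52 is at Week 36. A positive Week 52 result can therefore reflect conception before or after the last dose, and the site must date it before it knows whether the 24-hour duty applies.

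**Step 5: does another rule close the gap?** The SAE window of 30 days after the last visit reaches 52 + 30/7 = Week 56.3 in Groups 1 and 2 and 60 + 30/7 = Week 64.3 in Groups 3 and 4. The 12-week limit reaches Week 60. Within these windows, and later if the drug is suspected, a congenital anomaly is reportable (Section 7.2.1). Pregnancy itself is not on the SAE list, and a birth after conception at Week 54 would normally come well after these dates.

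**The case against.** Much of the case on the other side stands.

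- **The boundary is unclear.** A reader might infer that cover stops on the day of the Week 48 injection, leaving 20 weeks open. The documents do not compel that. Treatment Period 2 runs to Week 52, and a 6-weekly patient is then still within her dosing interval. The gap is firm only from Week 52.
- **The Week 52 test is not without consequence.** A reader might infer that positive tests after the last dose never have to be reported. That is wrong: Section 7.4 turns on when the pregnancy occurs, so a conception between Week 36 and Week 48 found at Week 52 is reportable.
- **Adverse outcomes are not simply lost.** Congenital anomaly is an SAE, SAEs during pregnancy go on the SAE form, and Section 7.1 tells patients to report later events thought related to the drug. This route is partial: it captures bad outcomes, not the pregnancy, its normal outcome or routine follow-up.
- **The form sentence in 7.4 does not repeat the limit.** One could read it as covering every pregnancy. It more naturally says how the pregnancies already defined are recorded.
- **The 20 weeks is an EU example** of a local labelling requirement, not a rule for all sites, and the Week 60 visit exists only in Groups 3 and 4.
- **No count can be given.** A reader might want the number of missed pregnancies. The documents state neither how many patients are women of child-bearing potential nor a pregnancy rate.

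None of this brings a Week 54 conception found at Week 60 within Section 7.4.

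**Conclusion.** The concern holds for conceptions after the end of treatment: from Week 52 in completers, and after the Week 24 visit in patients withdrawn then. These need not be reported or followed under Section 7.4, although the protocol's own testing or contraception text can extend to that time. For Week 52 positives the fault is narrower: whether the duty applies depends on dating conception against an undefined term.

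The uncovered time is 8 weeks in Groups 3 and 4 from the study schedule alone, and 16 weeks in any group where the EU example applies. In Groups 1 and 2 and in Week 24 withdrawals it exists only where local labelling extends contraception beyond the study. The Week 60 test concerns the women of child-bearing potential among about 210 planned patients (Section 9.7.1), so few events should be expected. These figures assume that being on study drug lasts to the end of the treatment period. This is a safety-reporting gap worth closing because closing it is cheap.

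**What to change.** Reconcile Section 7.4 with Section 6.5.6, Table 6-1 and criterion 9. Require reporting and outcome follow-up of every pregnancy the site learns of from first dose to the end of the contraception period that applies to that patient under criterion 9. Name expressly any positive test at Week 52, Week 60 or an early end-of-treatment visit, whether or not the patient is still taking drug. This removes the need to date conception before reporting and does not impose the EU period elsewhere.

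The cost is one sentence in the protocol, matching site instructions and a few more pregnancy forms, with no added test or visit. The limit should be stated openly: under the EU example the period ends 68 − 52 = 16 weeks after the last visit of Groups 1 and 2 and 68 − 60 = 8 weeks after that of Groups 3 and 4. Pregnancies in that time would be learned of only if the patient reports them, so patients should be told at their last visit to do so.

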8.1 Site monitoring

Before study initiation, at a site initiation visit or at an Investigator's meeting, a Novartis representative will review the protocol and eCRFs with the Investigators and their staff. During the study, the field monitor will visit the site regularly to check the completeness of patient records, the accuracy of entries in the eCRFs, the adherence to the protocol and to Good Clinical Practice (GCP), the progress of enrollment, and to ensure that study drug is being stored, dispensed, and accounted for as appropriate. Key study personnel must be available to support the field monitor during these visits.

In addition, monitoring of treatment accountability will be performed continuously by a field monitor during site visits and at the completion of the study. The field monitor will regularly check that study drug is being stored, prepared, dispensed and accounted as appropriate and ensure that only unblinded personnel would have access to.

The Investigator must maintain source documents for each patient in the study, consisting of case and visit notes (hospital or clinic medical records) containing demographic and medical information, laboratory data, ECGs, and the results of any other tests or assessments. All information on eCRFs must be traceable to these source documents in the patient's file. The Investigator must also keep the original ICF signed by the patient (a signed copy is given to the patient).

The Investigator must give the monitor access to all relevant source documents to confirm their consistency with the eCRF entries. Novartis monitoring standards require full verification for the presence of informed consent, adherence to the inclusion/exclusion criteria, documentation of SAEs, and of data that will be used for all primary variables.

Additional checks of the consistency of the source data with the eCRFs are performed according to the study-specific monitoring plan. No information in source documents about the identity of the patients will be disclosed.

